3.4.2.2 Additional Efficacy Analysis on the Change from the OLE Study baseline

The following additional analysis will be done for mNIS+7 score:

 Responder Analysis for mNIS+7 score described in section 3.4.2.1 based on the change in mNIS+7 score from the OLE study baseline will be performed. The efficacy analyses described in this section will be repeated using the OLE study PPS.

3.4.3 Other Efficacy Endpoints

Descriptive statistics, as described in section 3.4.1 (but without stratification by subgroup) will also be provided for the following efficacy endpoints:

- Change and percent change in mBMI and BMI from either the parent study baseline or the OLE study baseline to Week 78 and Week 156 in the FAS and PPS
- Shift table from either the parent study baseline or the OLE study baseline in PND score from to Week 78 and Week 156 in the FAS and PPS
- Change and percent change from either the parent study baseline or the OLE study baseline in NT-proBNP in the FAS, PPS, ECHO subgroup and CM-ECHO Set. Change in log-transformed NTproBNP from either the parent study baseline or the OLE study baseline to Week 78 and Week 156 in the FAS, PPS, ECHO subgroup and in the CM-ECHO Set
- Change and percent change in the SF-36 questionnaire domain scores, including Physical Component Summary Score, Mental Component Summary Score, and Mental Health Domain Score from either the parent study baseline or the OLE study baseline to Week 78 and Week 156 in the FAS and PPS
- Change and percent change from either the parent study baseline or the OLE study baseline to Week 78 and Week 156 in NSC in the FAS and PPS
- Change and percent change from either the **parent study baseline** or the **OLE study baseline** to Week 78 and Week 156 in the NSC individual domain scores (muscle weakness, sensory [hypo/loss of sensation], sensory [paresthesia, hyper sensation], autonomic [GI/urinary incontinence], and autonomic [other than GI//urinary incontinence]) in the FAS and PPS.

Analysis for ECHO will be included in a separate SAP for the following endpoints:

- Change and percent change in GLS by ECHO from either the parent study baseline or the OLE study baseline to Week 78 and Week 156 in the parent study ECHO subgroup, OLE ECHO set and in the Cardiomyopathy-ECHO (CM-ECHO) Set
- Change and percent change in the ECHO parameters (except GLS) in the parent study ECHO subgroup, OLE ECHO set and in the CM-ECHO Set from either the parent study baseline or the OLE study baseline to Week 78 and Week 156

Note that the 7 point change score (-3, -2, -1, 0, 1, 2, 3) that is recorded on the NSC questionnaire will be listed but not summarized or analyzed. Similarly for questions 20-29 the location is only listed. Questions 31-34 are of particular interest and therefore the number and percentage of patients responding 0 (No), 1 (slight +), 2 (moderate ++) or 3 (severe +++) will be presented.

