 - o For NSC and individual components, the parent study baseline will be defined as the average of two assessments taken within 60 days prior to the first dose of Study Drug in the parent study. If only one assessment has been done, the single assessment will be used in place of the average. Because NSC score is collected during the NIS assessment procedure in the parent study, it is possible it could be completed early in the treatment period rather than pre-treatment. These assessments will be included in the analysis as valid parent study baseline assessments provided they are taken within one week after the first dose of the parent study.
 - For ECG, the parent study baseline will be defined as the average of the triplicate taken on Day
 1 Pre-dose in the parent study. If only one or two assessments are available, the single

- assessment or average of the two assessments will be used. In the case that Day 1 Pre-dose is missing, screening visit results of the parent study will be used as baseline.
- The protocol permitted baseline ERG and ophthalmology examinations can be done up to one
 week after CS2 Study Day 1. Assessments done within one week of first dose will be included in
 the analysis as valid parent study baseline assessments.
- The **parent study baseline** laboratory assessment including PD will be defined as the average of all non-missing pre-dose assessments in the parent study.
- OLE study baseline will be defined as the last non-missing assessment prior to the first dose of ISIS 420915 in the OLE study (CS3 Study Day 1). However the last assessment must be collected within 3 months (90 days) before CS3 Study Day 1 of OLE study in order to be used to derive the baseline, i.e. if there is no assessment within 3 months, the OLE study baseline will be missing. Depending on when the assessments are scheduled to be collected this may be derived from the CS3 Study Day 1 or the screening visit in the OLE study or the last non-missing assessment from the parent study. Considerations for mNIS+7, NSC, and ECG are detailed below:
 - For mNIS+7 (and its individual components) and NSC (and its individual components), if the last assessment is the Week 66 assessment in CS2, the average of the two Week 66 assessments will be taken (as defined in the CS2 Statistical analysis plan). If only one assessment has been done, the single assessment will be used.

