In the parent study, two independent assessments of NSC are planned at the baseline visit and the Week 66 visit. A single NSC assessment is planned at the Week 35 visit. In this present OLE study, two independent assessments of NSC are planned at the Week 78 and 156 visit. A single NSC assessment is planned at the Week 26, 52, 104 and 130 visit. The mean of the two replicate assessments within a visit will be used for analysis of the parent study baseline, the parent study Week 66 visits (provided both visits fall in the visit window and are within 52 days of the last dose of medication), the OLE study Week 78 and 156 visit (provided both visits fall in the visit window and

are within 52 days of the last dose of medication). The individual questions scores will be averaged first. These will be referred to as the averaged question scores.

At the parent study baseline and Week 66 visits and the OLE study Weeks 78 and 156 visit, in the event that only one question has been performed, the single question will be used in place of the mean value for that visit for the averaged question score. If both of the questions are missing, the averaged question score is missing. At the parent study Week 35 visit, the OLE study Week 26, 52, 104 and 130 visit only one assessment is performed, therefore the single question will be used as the averaged question score for that visit. The sub-domain and domain scores will be computed using the averaged question scores

Imputing Missing Assessment averaged question Scores

The following imputation rule will be applied at the domain level for the sensory (hypo / loss of sensation), sensory (paresthesia, hyper sensation), autonomic (GI and urinary incontinence), and autonomic (other than GI/urinary incontinence) domains

- If at least 50% of the averaged question scores in the domain are available, the missing questions will be set to be equal to the mean of the non-missing averaged question scores in the domain. The total domain score is then calculated from the sum of the non-missing and imputed averaged question scores in the domain
- Otherwise, the domain score will be considered to be missing

Note for the imputation of the autonomic (other than GI/urinary incontinence) component in women, questions 35 and 36 are ignored and are not included in the imputation procedure

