8.2 Appendix 2 Scoring of Assessment Instruments

Neuropathy Symptoms and Change (NSC)

The NSC questionnaire consists of 38 questions asking about different symptoms.

A symptom is marked as present if in the judgment of the examining neurologist, it occurs more frequently or more severely than in healthy persons of the same age and gender and is due to

neuropathy. If a symptom is present its severity is graded as 1 (slight +), 2 (moderate ++) or 3 (severe +++). If the symptom is not present it is given a score of 0.

Two questions (35 and 36) are only answered by men. These are not included in the score for women.

The questions in the NSC can be divided into the following domains

Muscle weakness: Questions 1 - 19
 Sensory (hypo / loss of sensation): Questions 20 - 22
 Sensory (paresthesia, hyper sensation): Questions 23 - 29

• Autonomic (GI/Urinary incontinence): Questions 31, 32, 33, 34

• Autonomic (other than GI/Urinary incontinence): Questions 30, 35 - 38 for men

Questions 30, 37 - 38 for women

The Muscle weakness domain is also divided into 4 sub-domains:

Head and Neck: Questions 1 - 6
 Chest: Questions 7 - 9
 Upper Limbs: Questions 10 - 15
 Lower Limbs: Questions 16 - 19

For each sub-domain and domain the total score is obtained by summing the relevant questions. The maximum score is therefore 57 for muscle weakness, 9 for Sensory (hypo / loss of sensation), 21 for Sensory (paresthesia, hyper sensation), 12 for Autonomic (GI/Urinary incontinence), 15 for Autonomic (other than GI/Urinary incontinence) in men and 9 for Autonomic (other than GI/Urinary incontinence) in women. The minimum score is zero for each domain.

The NSC total score is the sum of the scores across all 5 domains. The minimum NSC total score is therefore 0 and the maximum NSC total score is 114 for men and 108 for women.

For questions 20-29 the location affected is also collected on the questionnaire but this information is not used in the calculation of the domain or total scores.

The NSC questionnaire also records a change score for the change in symptoms compared to the week before study onset. These are scored as follows

- -3 =worse ---
- -2 = worse --
- -1 = worse -
- 0 = no change
- +1 = better +
- +2 = better ++
- +3 = better +++

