9.2.2.3 Itegrated Summary of Efficacy based on CS2 and CS3 data

Descriptive summary statistics:

Descriptive summary statistics for absolute values, change or percent change from ISIS 420915 baseline, if applicable, will be provided by analysis visits for below endpoints based on 420915 FAS, unless specify.

- mNIS+7 Composite Score (On-Treatment)
- mNIS+7 Composite Score (On-Treatment) by IM
- Modified +7 and +7 Composite Scores (On-Treatment)
- NIS+7 Composite Scores (On-Treatment)
- NIS Composite and Component Scores (On-Treatment)
- Modified +7 Component Scores (On-Treatment)
- +7 Component Scores (On-Treatment)
- Norfolk QOL-DN Total Score (On-Treatment)
- Norfolk QOL-DN Total Score (On-Treatment) by IM
- Norfolk QOL-DN Symptoms Domain Score (On-Treatment) Stage 1 Patients
- Norfolk QOL-DN Physical Functioning/Large Fiber Neuropathy Domain Score (On-Treatment)
 Stage 2 Patients
- Norfolk QOL-DN Domain Scores (On-Treatment)
- NSC Total Score and Domain Scores (On-Treatment)
- Modified Body Mass Index and Body Mass Index (On-Treatment)
- Transthyretin (TTR) and Retinol Binding Protein 4 (RBP4) (On-Treatment)
- Transthyretin (TTR) (On-Treatment) by IM
- SF-36 Component Summary Scores and Domain Scores (On-Treatment)
- NT-proBNP Result (pmol/L) and Log-Transformed NT-proBNP Result (On-Treatment), outputs will be repeated based on ISIS 420915 CM-ECHO set
- mNIS+7, NIS+7, NIS, Modified +7, +7 Composite and Component Scores (Post-Treatment)
- Norfolk QOL-DN Total and Domain Scores (Post-Treatment)
- SF-36 Scores (Post-Treatment)
- NSC Score (Post-Treatment)
- Global Longitudinal Strain (%) (On-Treatment) based on ISIS 420915 Enrolled Patients, ISIS 420915 ECHO Subgroup, and ISIS 420915 CM-ECHO Set
- Assessment of Global Left Ventricular Size and Function LV Mass (g) (On-Treatment) based on ISIS 420915 Enrolled Patients, ISIS 420915 ECHO Subgroup, and ISIS 420915 CM-ECHO Set
- mNIS+7 Composite Score: Response Rate by Threshold Value by Visit (On-Treatment) based on ISIS 420915 FAS

- Summary of PND Score Shift from Baseline by Visit (On-Treatment) based on ISIS 420915
 FAS
- Summary of PND Score Change from Baseline by Visit (On-Treatment) based on ISIS 420915
 FAS
- Summary of Select Questions from NSC (On-Treatment) and (Post-Treament) based on ISIS 420915 FAS

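### SAP 3.4.3 tabulates NSC Questions 31-34 only as 0, 1, 2 or 3, but at visits with two assessments the SAP's own averaging gives half-point values that fit no category

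*Combined protocol and SAP*

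**What the plan says.** **Scale.** SAP Appendix 2 (8.2) scores each NSC question as an integer: "If a symptom is present its severity is graded as 1 (slight +), 2 (moderate ++) or 3 (severe" and so on, with 0 when the symptom is absent.

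**Number of assessments.** Under the NSC heading of SAP 3.2.1.3, the parent study has two assessments at baseline and at Week 66. In the OLE, "two independent assessments of NSC are planned at the Week 78 and 156 visit", whereas "A single NSC assessment is planned at the Week 26, 52, 104 and 130 visit".

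**Averaging.** The same section averages at question level, before any domain score is formed: "The individual questions scores will be averaged first. These will be referred to as the averaged question scores". If only one replicate exists, it is used alone.

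**Baselines.** SAP 3.2.1.1.2 states, for NSC and its components, that "the parent study baseline will be defined as the average of two assessments taken within 60 days prior to the first dose" in the parent study. The OLE baseline is the average of the two CS2 Week 66 assessments when Week 66 is the last assessment. Again, a single assessment stands alone.

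**What goes into tables.** SAP 3.2.1.3 has a general rule for replicated data: the patient's mean goes into tables and figures, and the individual values go into listings.

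**The table.** SAP 3.4.3 singles out Questions 31-34, the GI and urinary incontinence items, and says that "the number and percentage of patients responding 0 (No), 1 (slight +), 2 (moderate ++) or 3 (severe +++) will be presented".

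SAP 9.1 does not list this table among the analyses removed. None of these sections gives a rounding rule, a rule for choosing a replicate, or half-point rows.

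**The concern.** Two stated rules collide. One turns a four-grade item into a seven-value average at certain visits; the other reports the item in four grades at every visit. A programmer who follows both exactly has nowhere to put some patients. They could be left out of the rows, removed from the denominator, rounded up or rounded down. Each choice gives different percentages, and the SAP authorises none of them.

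The problem falls mainly on the visits with two assessments: parent baseline, CS2 Week 66 and OLE Weeks 78 and 156. A shift in the profile from Week 52 to Week 78, or from baseline to Week 26, could then reflect how many assessments were done and not any change in symptoms.

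**Working it through.** The plan gives no figure to reproduce, so the check is an enumeration followed by an illustration under stated assumptions.

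**Step 1: which averages are possible.** Inputs: two answers, each 0, 1, 2 or 3 (SAP 8.2), averaged (SAP 3.2.1.3). There are 4 × 4 = 16 ordered pairs.

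| Difference between answers | Ordered pairs | Average | Row in the 3.4.3 table |
|---|---|---|---|
| 0 grades | 4 | 0, 1, 2, 3 | yes, and correct |
| 1 grade | 6 | 0.5, 1.5, 2.5 | none |
| 2 grades | 4 | 1, 2 | yes, but a grade given at neither assessment |
| 3 grades | 2 | 1.5 | none |

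So 6 + 2 = 8 of 16 pairs have no row, and 3 of the 7 possible averages (0.5, 1.5, 2.5) have no category. Another 4 pairs are misplaced: 0 with 2 is shown as slight, and 1 with 3 as moderate. These are counts of possible pairs, not of patients, because in practice the pairs are not equally likely.

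**Step 2: what the unstated choice can do to one row.** The documents give neither the share of patients answering No nor the disagreement between assessments. Assume that 70% answer No at a single assessment, that a share *d* of patients answer 0 once and 1 once (equally often in either order), and that no other disagreement occurs. Then:

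- average exactly 0: 70 − *d*/2. This is the No row if half-points are rounded up, or are left out of the rows but kept in the denominator;
- rounded down: 70 + *d*/2;
- removed from the denominator: (70 − *d*/2) / (100 − *d*).

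| *d* (assumed) | Rounded up, or no row | Rounded down | Removed from denominator |
|---|---|---|---|
| 5% | 67.5% | 72.5% | 67.5/95 = 71.1% |
| 10% | 65.0% | 75.0% | 65/90 = 72.2% |
| 20% | 60.0% | 80.0% | 60/80 = 75.0% |
| 30% | 55.0% | 85.0% | 55/70 = 78.6% |

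A single-assessment visit would show 70.0% in every line. If half-points are left out of the rows but kept in the denominator, the four rows add to 95%, 90%, 80% or 70%.

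**Step 3: cross-check with a different model.** Assume that the two answers are cut points on correlated normal variables. With 70% answering No and correlation 0.90, about 20% of patients have a half-point average and about 63.7% average exactly 0. Over wider assumptions (50% to 90% answering No, correlation 0.98 to 0.70), the half-point share runs from about 4% to about 36%. It also depends on how the remaining answers split among grades 1 to 3: at 50% No and correlation 0.95, it is 16% to 23%. This range only shows how open the size is.

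**The case against.** **The table could mean the raw answer, since it speaks of patients responding.** This does not resolve the conflict. A patient with two different answers would belong in two rows, with no rule for which counts, and SAP 3.2.1.3 sends the mean, not the raw values, to tables.

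**The consequence is small.** This stands. The table is descriptive, SAP 1.3 states no formal hypotheses, NSC is not among the protocol's listed objectives or endpoints, and all raw answers appear in listings. Domain and total scores accept fractional values without difficulty.

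**Single-assessment visits are not clean either.** This also stands. A reader might infer that Weeks 26, 52, 104 and 130 always give integers. SAP 3.2.1.3 averages any extra replicates, averages two visits equally near the target day, and imputes missing questions from the domain mean without saying whether imputed values enter this table. Those visits normally give integers, but not always.

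**The final analysis may differ.** A reader might infer that section 9 carries the four-category table forward unchanged. SAP 9.2.2.3 lists only "Summary of Select Questions from NSC (On-Treatment) and (Post-Treament) based on ISIS 420915 FAS", under a heading about absolute values and changes. It names neither Questions 31-34 nor the categories, and 9.2.2 refers details to a separate ISS SAP that is not available here. SAP 9.2.1 lists selected NSC questions for analysis of change and, post-treatment, for numeric summaries, which can hold half-points. So the conflict is established for 3.4.3 only.

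**Other remedies exist.** A stated rounding direction, the worse replicate or added half-point rows would also remove the undefined step. Rounding or half-point rows, however, would leave two-assessment visits on a different footing from the others.

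**Conclusion.** The conflict holds for the Question 31-34 frequency table in SAP 3.4.3. It follows from the text alone and needs no assumption: averages of 0.5, 1.5 and 2.5 have no category, and answers two grades apart are shown as a grade given at neither assessment. Percentages at parent baseline, CS2 Week 66 and OLE Weeks 78 and 156 are incomplete or distorted whenever the two answers differ, and so are not comparable with Weeks 26, 52, 104 and 130.

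The size is unknown. The figures under working rest on an assumed share answering No and an assumed disagreement. It would be tempting to multiply such a share by 135, but that is the approximate number planned for the parent study, not the number with two NSC assessments at Week 78 or 156.

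Nor is it supported to say that both baselines are always averages. The OLE baseline is a two-assessment mean only when CS2 Week 66 is the last assessment and both replicates exist; the parent baseline is one only when both were done.

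This is worth correcting, but it bears on no test and on no NSC domain or total score.

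**What to change.** Add one sentence to SAP 3.4.3: the Question 31-34 frequency tables use one observed, unaveraged and unimputed response per patient per visit, at every visit and at both baselines (for example, the first assessment in the analysis window). Word it as an explicit exception to the duplicate-mean rule in 3.2.1.3. Keep the averaged question scores for NSC domain and total scores. Apply the same rule to any categorical output of selected NSC questions under section 9.

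The cost is one SAP sentence and a small programming change, with no new data. The downside is that these four tables do not use the second replicate; it still contributes to the domain and total scores and appears in the listings.

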3.5 Pharmacodynamic (PD) Analyses

Descriptive statistics as described in section 3.4.1 (but without stratification by subgroup) will also be provided the following PD endpoints:

- Change and percent change in TTR level from either the parent study baseline or the OLE study baseline to Week 78 and Week 156
- Change and percent change in RBP4 level from either the **parent study baseline** or the **OLE study baseline** to Week 78 and Week 156.

In addition the proportion of patients with percentage decrease from either the **parent study baseline** or the **OLE study baseline** in plasma transthyretin (TTR) \geq 60% will be summarized by parent study treatment group at each visit.

As not all subjects will get to year 4 and 5 of the study, data from year 4 and 5 will be summarized as described in section 3.4.1.

3.6 Pharmacokinetic (PK) and Immunogenicity (IM) Analyses

PK endpoints include the following:

Plasma trough and post-treatment levels of ISIS 420915 in all evaluable patients in the OLE study
 PK set

IM endpoints include the following:

- IM status [confirmed positive/negative or unevaluable and, when applicable, titer of anti-ISIS
 420915 antibodies (ADA)] in all patients in the OLE study SS
- IM status (positive, negative or 'unknown') and its characteristics if applicable (onset, duration, peak titer, time to reach peak titer, etc.) in the OLE study SS

Plasma samples will be collected at protocol designated times for ISIS 420915 plasma PK and IM assessments.

3.6.1 Plasma Pharmacokinetics

Plasma concentrations of ISIS 420915 will be summarized at interim analyses and final analysis at EOS of the OLE study.

Plasma concentrations of ISIS 420915, along with the scheduled (nominal) and actual sampling times (i.e., time from subcutaneous dosing) will be listed for each evaluable patient by treatment group of the parent study, actual dose, gender, patient immunogenicity (IM) status, and study day. Plasma concentrations below the lower limit of quantification (LLOQ) will be indicated by "BLQ". Percent differences between nominal and actual dose, as well as between scheduled and actual sampling times will also be listed for all patients.

ISIS 420915 plasma trough (predose) concentrations will be summarized using descriptive statistics by dose, study day, and scheduled time point, without and with stratification by prior treatment in the parent study and patient IM status (see Section 3.6.2). For the purpose of calculating typical summary descriptive statistics (n, mean, SD, %CV, geometric mean, geometric %CV, percentiles (e.g., median, P25, and P75), minimum, and maximum) for plasma concentrations, all BLQ values will be set to zero. Mean plasma concentrations that are below the LLOQ will be presented as BLQ, and the SD, SE, and %CV will be reported as not applicable. Other stratifications may also be

performed if deemed warranted to properly interpret the pharmacokinetic analysis. Samples will be excluded from descriptive statistics if there are large deviations between scheduled and actual sampling times (percent difference between scheduled and actual sampling time greater than 30%), or large deviations between actual dose and nominal dose (percent difference between nominal and actual dose greater than 30%). Any samples excluded from the summary descriptive statistics, if deemed necessary, will be listed separately along with the reason for exclusion.

For all evaluable patients, ISIS 420915 plasma trough (predose) concentrations versus time (actual) profiles for each individual patient, as well as corresponding mean (±SD) plasma concentration versus time (scheduled) profiles will be presented graphically on linear and semilogarithmic scales, without and with stratification by prior treatment in the parent study and patient immunogenicity status (see Section 3.6.2). Other stratifications may also be performed if deemed warranted. At the discretion of the pharmacokineticist and/or biostatistician, samples may be excluded from the mean plots if there are large deviations between scheduled and actual sampling times, or large deviations between actual dose and nominal dose.

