3.2.1 Analysis Conventions

All reporting will be performed in SAS version 9.3 or higher.

Efficacy results will be summarized under the treatment to which patients were randomized in the parent study. Safety and PK results by treatment group of parent study will be summarized under the treatment to which patients received in the parent study. Should there be any cases after the parent study unblinding in which a patient received treatment other than what was randomized, such cases will be discussed in the OLE study report and noted in footnotes where applicable.

All electronic case report form data, lab data transfers, ECHO, ECG, and mNIS+7 score data, as well as any outcomes derived from the data, will be provided in the patient data listings. Patient data listings will be presented for all patients enrolled into the OLE study, will include all data collected during the OLE phase, and will be sorted by treatment group of parent study, patient ID, visit, and time point (where appropriate).

Central laboratory assessments will be included in the summary tables; local laboratory assessments will only be included in listings. Exceptions to the use of local laboratory assessment in summary tables are made for platelets, where summary tables will use both local and central laboratory results.

[figure not shown]
All tables will present the population frequencies in each treatment group in the parent study and/or subgroup (where appropriate) and will indicate the number of patients with non-missing data and the denominators for percentages.

Descriptive summary statistics including n, mean, percentiles (e.g., median, 25th percentile [P25], and 75th percentile [P75]), standard deviation, and range (minimum, maximum) for continuous variables, and counts and percentages for categorical variables, will be used to summarize data by treatment group of the parent study. Summaries of PK parameters, if applicable, will also present geometric mean, standard deviation of log-transformed data, and coefficient of variation, expressed as a percent (%CV). Where appropriate, p-values will be reported. All statistical tests will be conducted using 2-sided tests with a 5% Type I error rate, unless otherwise specified.

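### SAP 3.6.1 sets BLQ troughs to zero for the geometric mean and geometric %CV as well, a rule that fails in any cell mixing BLQ and quantifiable values

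*Combined protocol and SAP*

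**What the plan says.** SAP 3.6.1 (Plasma Pharmacokinetics) defines the summary of plasma concentrations as "typical summary descriptive statistics (n, mean, SD, %CV, geometric mean, geometric %CV, percentiles (e.g., median, P25, and P75), minimum, and maximum) for plasma concentrations" and, in the same sentence, says that for calculating them "all BLQ values will be set to zero". The geometric statistics are not exempted.

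The next sentence is a display rule: "Mean plasma concentrations that are below the LLOQ will be presented as BLQ, and the SD, SE, and %CV will be reported as not applicable". It does not mention the geometric mean or geometric %CV.

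Trough summaries are produced by dose, study day and time point, "without and with stratification by prior treatment in the parent study and patient IM status". SAP 3.2.1 (Analysis Conventions) says that PK parameter summaries "will also present geometric mean, standard deviation of log-transformed data, and coefficient of variation", with no rule for zeros. The PK outputs added for the final analysis in SAP 9.2.1 and 9.2.2.4 bring in further trough tables but no BLQ rule.

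**The concern.** The rule and part of the list it governs cannot both be carried out. One zero in a cell removes the geometric %CV and turns the geometric mean into zero or an undefined value. This is a stated instruction that fails, rather than a detail left open.

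Plasma trough level is a stated secondary objective, and the tables are split by prior treatment and antibody status. Without a workable rule each programmer has to improvise, and the reader cannot tell what was done. If the improvised answer is to leave the zeros out, strata with different BLQ shares are distorted by different amounts.

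**Working it through.** The plan states no PK figure to reproduce, so the check is by definition, then by example.

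**Formulas.** Geometric mean (GM) = exp(mean of ln x), equivalently (product of x)^(1/n). Geometric %CV = 100 × sqrt(exp(var(ln x)) − 1). Since ln 0 does not exist, one zero gives GM = 0 by the product form or an undefined value by the log form. Geometric %CV is undefined either way.

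**A mixed cell (assumed values 20, 30, 40, 50, 60 and one BLQ).**
- Zero kept: GM = 0, geometric %CV undefined, arithmetic mean = 200/6 = 33.3.
- Zero dropped: GM = (20 × 30 × 40 × 50 × 60)^(1/5) = 37.3 and geometric %CV = 45.5%, both on 5 values. They would sit beside an arithmetic mean of 33.3 on 6 values. A GM above the arithmetic mean is impossible on one set of data, so the row would contradict itself.

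**Where mixed cells are foreseeable.** Protocol Appendix A schedules a pre-dose trough at Week 1 Day 1, and SAP 3.2.1.4 starts the PK tables at CS3 Study Day 1. Former-placebo patients have had no drug by then (Protocol 4.2; SAP 3.2.1.1.1). SAP 1.1 gives 90 active and 45 placebo patients as planned, so if all enrolled, 45/135 = one third of the unstratified Day 1 cell would be zeros. Post-treatment levels are a PK endpoint (SAP 3.6), and Appendix A has a sample 13 weeks after the last dose. BLQ values there are possible, but no rate is given.

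**Chance that a cell holds at least one BLQ value**, 1 − (1 − p)^n, assuming independent patients and an assumed BLQ rate p:

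| n | p = 1% | p = 2% | p = 5% |
|---|---|---|---|
| 45 | 36% | 60% | 90% |
| 90 | 60% | 84% | 99% |
| 135 | 74% | 94% | 99.9% |

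**Effect if zeros are dropped** (assumed lognormal troughs, true GM = 1, BLQ values being the lowest):

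| BLQ share | GM, true CV 50% | Geometric %CV | GM, true CV 100% | Geometric %CV |
|---|---|---|---|---|
| 5% | 1.05 | 45% | 1.10 | 87% |
| 10% | 1.10 | 42% | 1.18 | 80% |
| 25% | 1.22 | 36% | 1.42 | 67% |
| 50% | 1.46 | 29% | 1.94 | 54% |

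Dropping biases the GM up and the geometric %CV down.

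**Effect of substituting half the lower limit of quantification (LLOQ/2)**, same assumptions. At 10% BLQ the GM is 0.95 and geometric %CV 61% (true CV 50%), or 0.97 and 108% (true CV 100%). At 25% BLQ the figures are 0.90 and 66%, or 0.95 and 107%. The GM is closer to the truth, but the geometric %CV is overstated.

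The substitute can matter more when the LLOQ lies far below the other values. Take nine values of 50 and one BLQ with LLOQ 1 (assumed). LLOQ/2 gives GM = exp((9 ln 50 + ln 0.5)/10) = 31.5. The variance of ln x is (ln 100)² × 0.9/9 = 2.12, so geometric %CV = 100 × sqrt(exp(2.12) − 1), about 271%. The arithmetic %CV with the zero kept is 15.8/45 = 35%.

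**The case against.** The strongest reply is that the display rule already deals with the clearest case. In former-placebo patients at Day 1 every value should be BLQ, the mean is zero, and the table shows BLQ with dispersion not applicable. That stands as to intent, although the geometric statistics are not named. The rule does not settle mixed cells. If the arithmetic mean is above the LLOQ it is not triggered. If it is stretched to a geometric mean of zero, the cell prints BLQ even though most of its patients may have quantifiable levels.

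It can also be said that the unstratified Day 1 cell pools unexposed and treated patients, so its geometric mean means little, and that the stratified table is required as well. That is fair, but the plan still orders the pooled cell. Arithmetic mean, median, quartiles and range remain computable, and individual values are listed with BLQ marked, which limits the harm.

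A reader might infer more than the documents support:
- **That the geometric statistics fail throughout.** Only cells with a BLQ value are affected. Dosing is weekly, and the one half-life given (17.0 days in plasma, nonclinical, Protocol 2.3.3) does not suggest frequent BLQ troughs at steady state, though it does not exclude them.
- **That the plan drops zeros and so biases the geometric mean.** It does not say so. SAP 3.2.1 specifies SAS, which returns a missing value for log(0), so dropping is a likely programming result. SAP 3.6.1 does provide for listing excluded samples, in the context of dose and timing deviations.
- **That the log-scale profiles share the fault.** Concentration profiles "will be presented graphically on linear and semilogarithmic scales", but the zero rule is confined to summary statistics, so it does not set BLQ points in individual plots to zero. The mean profiles use the arithmetic mean, which is positive whenever any value in the cell is quantifiable.

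**Conclusion.** The point holds for cells that mix BLQ and quantifiable values. There the rule in SAP 3.6.1 makes the geometric mean zero or undefined and the geometric %CV undefined, and nothing else in the SAP repairs it. This follows from the definitions and rests on no assumption.

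The extent does rest on assumptions. The unstratified Day 1 cell should be affected, and post-treatment cells may be. For steady-state visits the number of affected cells is unknown, because neither the LLOQ nor an on-treatment BLQ rate is given. The bias figures are conditional on zeros being dropped and on lognormal troughs with the CVs and BLQ shares shown.

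The severity is minor: trough PK is descriptive, and SAP 1.3 states no formal hypotheses.

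**What to change.** Amend SAP 3.6.1 as follows.

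1. Keep zero for BLQ values in the arithmetic statistics and percentiles.
2. Exempt the geometric mean and geometric %CV from the zero rule and apply one pre-stated rule instead. Options are 'not calculated' when any, or more than a stated share, of the values in the cell are BLQ; a positive substitute such as LLOQ/2; or a censored-data estimate. The documents give no basis for preferring one. If substitution is chosen, note that it can distort the geometric %CV.
3. Print the number and percent BLQ in each cell.

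The cost is a sentence or two in the SAP and minor programming. The downside is that some cells will read 'not calculated' or will depend on a convention.
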